## **7.2 Analysis Populations**

The full analysis population was an intention to treat analysis, including all subjects who were randomised and received any study drug after consent.

The safety population was all subjects who received any study treatment (including control) but excluding subjects who drop out prior to receiving any treatment.

Prior to breaking the blind, each subject's inclusion or exclusion status with regard to each analysis population was established. The exact process for assigning the statuses was defined and documented prior to breaking the blind along with any predefined reasons for eliminating a subject from a particular population.

## **7.3 Covariates and Subgroups**

Covariates that may have an influence on the end points listed include gender, BMI, age and treatment order received i.e. placebo/empagliflozin versus empagliflozin/placebo. As the study is a crossover in design, the treatment order was included in the initial analysis as a covariate to ascertain if the intervention being investigated has a sustained effect on the primary outcome despite the 2 week washout period. These demographic subgroups were analysed for different treatments effects (for example comparison of effects by age, gender, BMI and treatment order). Where possible forest plot figures were used to communicate the relevant information about possible subgroup effects and interactions.

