## 6 Sample Size

Power calculations were based on our previous data in participants with CHF as well as more contemporary data. The sample size was based on the mean furosemide-induced urinary volume (SD=250). A 20% increase is expected in this parameter following SGLT2 inhibition. This increase in urinary volume is based on published percentage increases in urinary volume in T2D patients that range from 11%–33% depending on the dose of the SGLT2 inhibitor as shown by List and colleagues in the available data with dapagliflozin (dapagliflozin 2.5 mg: 11% increase in 24-hr urine volume; dapagliflozin 5 mg: 22% 11% increase in 24-hr urine volume; dapagliflozin 10 mg: 24% 11% increase in 24-hr urine volume; dapagliflozin 20 mg: 27% 11% increase in 24-hr urine volume and dapagliflozin 50 mg: 33% 11% increase in 24-hr urine volume). There is no data of SGLT2 inhibition together with loop diuretics apart from a case report of a diuretic resistant HF patient in whom the fluid overload was successfully treated with the SGLT2 inhibitor, ipragliflozin. The authors reported a striking 50% increase in urinary volume (following treatment with 50 mg daily of oral ipragliflozin for 5 days). Based on the above, it was determined that a 20% increase in furosemide induced increase in urinary volume was reasonable.

With an alpha 0.05 and power of 90%, 22 participants per arm are required, assuming 35% drop out. Since this trial is using an AB/BA crossover design, a total of 34 participants was required, as each participant was exposed to both arms of the trial. The rationale for the high dropout rate, was due to the high intensity renal physiological tests that will occur on 4 occasions for the participants, from 0830 to 1330 we feel that anything less than a 35% drop out rate would be conservative.

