### **9 Efficacy Analyses**

Efficacy analysis was performed on the intention to treat population as defined in section 7.2.

Data for continuous outcome measures were assessed for normality prior to analysis. Transformation of the outcome variables was used where necessary where these were not normally distributed. Outcome measures were assessed by 2 way Analysis of Variance (ANOVA). Initial comparison was between treatment groups (empagliflozin

vs placebo) at the final visit of each treatment arms (visit 5 and visit 9) adjusted for baseline measures (visit 2 and visit 6) of the outcomes.

Where data was not normally distributed and could not be transformed into a normal distribution, data were analysed using non–parametric methods. Data for categorical outcomes measures were assessed by logistic regression in the same way as described for continuous outcome measures.

All efficacy variables were listed by subject within study centre. Data were summarised by treatment group. Number, Mean, Standard Deviation, Minimum and Maximum will summarise continuous efficacy variables, whereas number and percent will summarise categorical efficacy variables.

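### SAP 7.3 reads treatment order as a carryover check and as a subgroup; in this AB/BA trial the first has little power and the second is a period effect plus any carryover

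*SAP*

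**What the plan says.** SAP 7.3 gives treatment order two jobs. First, "the treatment order was included in the initial analysis as a covariate to ascertain if the intervention being investigated has a sustained effect"; the question there is whether the drug still influences the primary endpoint after two weeks off treatment. Second, order is grouped with participant characteristics for examining whether the treatment effect varies, the example given being "comparison of effects by age, gender, BMI and treatment order". The display is specified too: "Where possible forest plot figures were used to communicate the relevant information about possible subgroup effects and interactions".

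SAP 9 names a two-way ANOVA for the outcomes, comparing treatments at visits 5 and 9 with adjustment for baselines at visits 2 and 6. It does not say what the two factors are and mentions neither a period term nor a participant term. SAP 5.4 defines the primary endpoint as 24-hour urine volume at the end of treatment, and its schedule places that collection at visits 3, 5, 7 and 9 only.

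On size, SAP 6 states: "With an alpha 0.05 and power of 90%, 22 participants per arm are required, assuming 35% drop out". It continues: "Since this trial is using an AB/BA crossover design, a total of 34 participants was required".

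**The concern.** In an AB/BA trial each participant has only one order, so the order term is a between-participant comparison and loses the precision that the crossover was chosen to give. If it is the means of judging whether empagliflozin still acts in the second period, a null result will probably appear whether or not carryover exists. Carryover would meanwhile pull the treatment estimate towards zero.

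The subgroup use raises a different problem. Order is not a participant characteristic. Splitting the treatment effect by order rearranges the same four sequence-by-period means so that a difference between periods looks like a difference in drug response. Period differences are plausible here: Protocol 3.1 foresees an insulin reduction on the day of randomisation with later titration. A forest plot with an order row beside age and BMI invites the reader to see effect modification where there is only a period shift.

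**Working it through.** **Plan's own figure.** 22 / (1 − 0.35) = 33.8, rounded up to 34. This matches SAP 6. The 22 itself cannot be checked, because the control mean to which the 20% increase applies is not given. Solving back with SD 250, two-sided alpha 0.05 (sidedness is not stated) and 90% power:

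- paired, normal: 250 × (1.960 + 1.282) / √22 = 173; paired *t*: 181
- two-sample, 22 per arm: 250 × 3.242 × √(2/22) = 244

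I therefore take an effect of 181 to 250 as an assumption.

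**Other inputs.** SD 250 (SAP 6; not stated whether it is the SD of the outcome or of the within-participant difference, so both are shown). 1:1 allocation is assumed, as the ratio is not stated: 11 v 11 completers, or 17 v 17 if all 34 are analysed. Within-participant correlation ρ is not given; 0.3 to 0.7 is assumed.

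**What the contrasts estimate.** Let τ be the treatment effect, π period 2 minus period 1, and λ the carryover of empagliflozin into period 2.

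| Order | Period 1 | Period 2 | Total | Empagliflozin − placebo |
|---|---|---|---|---|
| Empagliflozin/placebo | τ | π + λ | τ + π + λ | τ − π − λ |
| Placebo/empagliflozin | 0 | π + τ | τ + π | τ + π |

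- Totals differ between orders by λ. This is the carryover test.
- Treatment effects differ between orders by −(2π + λ). This is the order subgroup contrast.
- The average of the two treatment effects is τ − λ/2.

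**Power of the carryover test.** The SD of a participant's total is σ√(2(1 + ρ)), with σ = 250 if that is the outcome SD, or σ = 250/√(2(1 − ρ)) if it is the SD of the difference. The noncentrality is λ / (SD of total × √(2/g)), with g per order. For example, with outcome SD 250 and ρ = 0.5, the SD of the total is 433; with λ = 181 and g = 11 the noncentrality is 181 / (433 × 0.426) = 0.98, and power on 20 df is 15.4%. With λ set to the whole assumed effect:

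| SD 250 read as | λ | 11 v 11, ρ = 0.3 / 0.5 / 0.7 | 17 v 17, ρ = 0.3 / 0.5 / 0.7 |
|---|---|---|---|
| outcome SD | 181 | 17.1 / 15.4 / 14.2% | 24.6 / 21.9 / 19.9% |
| outcome SD | 250 | 28.3 / 25.2 / 22.8% | 41.8 / 37.2 / 33.5% |
| SD of difference | 181 | 22.0 / 15.4 / 10.4% | 32.4 / 21.9 / 13.8% |
| SD of difference | 250 | 37.4 / 25.2 / 15.5% | 54.6 / 37.2 / 22.1% |

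For a carryover half that size, the ranges are about 6% to 13% (11 v 11) and 7% to 18% (17 v 17).

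Simulation (20,000 trials, 11 v 11, ρ = 0.5, true effect 181) shows the consequence. Full carryover cut the treatment estimate from 181 to 91, as τ − λ/2 predicts, and the order test was significant in 16% of trials.

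**Order as a subgroup.** Take a constant treatment effect, no carryover and a period shift of 100. The contrast between orders is 2 × 100 = 200 in size. With outcome SD 250, the within-participant difference has SD 250√(2(1 − ρ)) = 296, 250 and 194 for ρ = 0.3, 0.5 and 0.7. With 11 v 11 the interaction is significant at 5% in 32.7%, 43.1% and 63.5% of trials. In simulation at ρ = 0.5, the two order rows averaged 80 and 281, although the true effect was 181 for everyone; the average of the two rows stayed at 181.

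**The case against.** Several points on the other side are fair.

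- **A sequence term is not wrong.** It is a normal part of a crossover model. This stands; the fault is the conclusion that SAP 7.3 proposes to draw from it.
- **The size rests on assumptions.** The absolute effect, the correlation and the meaning of SD 250 are not in the documents, and that SD was planned for furosemide-induced volume, not for the 24-hour endpoint. This stands, and is why ranges are given. The highest figure, 55%, needs no dropout, the lowest assumed correlation and a carryover as large as the drug effect.
- **Low power assumes the correct error term.** If order were tested against a residual that ignores pairing, simulated type I error is 11% at ρ = 0.5 and 15% at ρ = 0.8. That misleads in the other direction and does not rescue the check.
- **Period-specific baselines are planned.** Adjustment for visits 2 and 6 could absorb some period shift for outcomes measured there. It cannot do so for 24-hour volume, which is collected at neither visit.

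Two stronger readings are tempting. A reader might infer from the words about an initial analysis that the SAP follows the two-stage crossover procedure, using only period 1 if order is significant. The SAP gives no threshold, no decision rule and no such fallback, and SAP 9 applies the word initial to the main treatment comparison. A reader might also infer that period is left out of the model. SAP 9 does not name the two factors, so period may be one of them; this is a gap in specification, not a demonstrated omission.

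**Conclusion.** The concern holds for the two uses stated in SAP 7.3. As a carryover check, order has a power of about 10% to 37% with 22 completers and 14% to 55% with all 34, even when carryover equals the whole assumed effect. The assumptions are 1:1 allocation, two-sided 5%, an effect of 181 to 250, ρ of 0.3 to 0.7, and either reading of SD 250. The figures show how little leverage the design gives and should not be quoted as power for the 24-hour endpoint. The conclusion that a non-significant order term cannot establish absence of carryover does not depend on the exact values.

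As a subgroup, the order contrast is −(2π + λ) by algebra, whatever the SD: exactly twice the period effect if there is no carryover, and a mixture otherwise. In neither case is it effect modification by a participant characteristic. That the results would be misread is an inference, but it follows from the purposes that SAP 7.3 states. The documents do not support a claim of type I error inflation from a pretest.

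**What to change.** In SAP 7.3:

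- Remove treatment order from the subgroup list and from the forest plot.
- State that absence of carryover will not be inferred from the order term.

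In SAP 9:

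- Specify treatment and period as fixed effects and participant as a random effect, fitted whatever the order result. A sequence term may stay in the model.
- Report the estimated period effect as a period effect.

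For carryover, argue from the length of the washout. Support this descriptively by comparing visit 6 with visit 2, separately by sequence, for weight, creatinine, eGFR and cystatin C, which the protocol schedule (Appendix 1) provides at both visits. A comparison pooled over sequences would mix carryover with time trend. HbA1c is scheduled at visit 1 and not at visit 2, so it can be compared only with screening. State plainly that no such check exists for the primary 24-hour urine volume, because it is not collected at visits 2 or 6.

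The cost is SAP wording and a few descriptive tables from data already scheduled. No new data are needed.

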## **7.4 Missing Data**

Missing values represent a potential source of bias in a clinical trial. Therefore every effort should be undertaken to fulfil all requirements of the protocol concerning the collection and management of data. The extent of the missing data was examined and the reason for drop–out ascertained. Multiple imputation was used to impute missing values where necessary and where assumptions for missing at random (MAR) data were met.

## **8 Summary of Study Data**

[figure not shown]
All continuous variables were summarised using the following descriptive statistics: n (non–missing sample size), mean, standard deviation, median, maximum and minimum. The frequency and percentages (based on the non–missing sample size) of observed levels were reported for all categorical measures. In general, all data were listed, sorted by site, treatment and subject, and when appropriate by visit number within subject. All summary tables were structured with a column for each treatment in the order (Intervention, Control) and was annotated with the total population size relevant to that table/treatment, including any missing observations.

Baseline characteristics for patients are: age, gender, past medical history, BMI, smoking history, blood pressure, HbA1c, eGFR, medication classes, severity of heart failure as identified by the ejection fraction (mild, moderate or severe), and medication classes.

Concurrent illnesses and medical conditions were recorded and listed but not analysed.

Patient medication was recorded at baseline and at each study visit. Anti–diabetic, diuretic and anti–hypertensive drug classes were reported.

### **8.1 Subject Disposition**

From the CRF it was established how many subjects reached what stage of the trial, how many dropped out and for what reasons (death, toxicity, treatment failure, withdrew consent). It was therefore identified the number screened, randomised, completed treatment 1, completed treatment 2, and ultimately how many completed the study.

## 8.2 Protocol Deviations

Specific protocol deviations that could impact the analysis of the trial include those entered into the study even though the subject did not satisfy the entry criteria, the development of withdrawal criteria during the study but were not withdrawn, or those who received the wrong treatment or incorrect dose.

### **8.3 Demographic and Baseline Variables**

Demographic variables that were recorded at the screening visit prior to randomisation were:

- Age
- Gender
- Concurrent Illnesses and Medical Conditions
- BMI
- Smoking history
- Alcohol intake (units/week)
- Severity of heart failure as identified by the ejection fraction (mild, moderate or severe) on echocardiogram
- Medication classes

All baseline variables that were recorded at the screening visit prior to randomisation include:

- blood pressure
- pulse
- weight
- BMI

- HbA1c
- eGFR
- Serum creatinine
- Urine Protein/Creatinine Ratio
- Urine Albumin/Creatinine Ratio

#### **8.4 Prior and Concurrent Medications**

Patient medication was recorded at baseline and at each study visit. Anti-diabetic, diuretic and anti-hypertensive drug classes were reported.

#### **8.5 Treatment Compliance**

The calculation of adherence was performed and reported as a percentage, where the number of tablets issued minus the number of drugs returned, was then divided by the number of drugs that should have been taken. This was performed by the PI at visit 3 and visit 7, and by the Pharmacy department at visit 5 and visit 9.

Adherence of 80–120% will be deemed as being compliant. Where an issue of non-compliance was evident, a sensitivity analysis was performed and adherence was included as a covariant.

### **9 Efficacy Analyses**

Efficacy analysis was performed on the intention to treat population as defined in section 7.2.

Data for continuous outcome measures were assessed for normality prior to analysis. Transformation of the outcome variables was used where necessary where these were not normally distributed. Outcome measures were assessed by 2 way Analysis of Variance (ANOVA). Initial comparison was between treatment groups (empagliflozin

vs placebo) at the final visit of each treatment arms (visit 5 and visit 9) adjusted for baseline measures (visit 2 and visit 6) of the outcomes.

Where data was not normally distributed and could not be transformed into a normal distribution, data were analysed using non–parametric methods. Data for categorical outcomes measures were assessed by logistic regression in the same way as described for continuous outcome measures.

All efficacy variables were listed by subject within study centre. Data were summarised by treatment group. Number, Mean, Standard Deviation, Minimum and Maximum will summarise continuous efficacy variables, whereas number and percent will summarise categorical efficacy variables.

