## 9.1 Primary Efficacy Analysis

The primary outcome measure was analysed in the same manner as described above and presented as the between treatment group difference in change in urine volume between the baseline and final visits.

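### SAP section 9 checks the outcome data for normality, not the crossover residuals, and lets the result choose the scale and method of the primary analysis

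*SAP*

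**What the plan says.** SAP section 9 sets out a sequence of three steps. First, "Data for continuous outcome measures were assessed for normality prior to analysis". Second, "Transformation of the outcome variables was used where necessary where these were not normally distributed". Third, "Where data was not normally distributed and could not be transformed into a normal distribution, data were analysed using non–parametric methods". The default is a two-way analysis of variance whose factors are not named, comparing treatments at visits 5 and 9 and "adjusted for baseline measures (visit 2 and visit 6) of the outcomes". SAP section 7.3 adds that "the treatment order was included in the initial analysis as a covariate".

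The sequence covers the primary endpoint. Section 9.1 says "The primary outcome measure was analysed in the same manner as described above", and section 9.2 extends it to all secondary outcomes.

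Neither document names the normality test or its threshold, the transformation, or the non-parametric test. Neither mentions model residuals or within-participant differences as the thing to check. Nothing says whether the fallback keeps the pairing or the treatment-order term. Protocol section 9.2.1 says only that analysis of variance is used for repeated measurements.

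**The concern.** The normality assumption of a crossover analysis concerns the within-participant error. Each participant's habitual urine volume enters both treatment periods and drops out of the empagliflozin-placebo contrast. A skewed mix of high-volume and low-volume participants therefore says nothing about whether the planned model is valid, yet it can make the pooled or per-treatment outcomes look non-normal.

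Under section 9 that appearance decides how the primary result is analysed and on which scale. A log transformation turns a difference in volume into a ratio. A rank method has no stated effect estimate. If the unnamed rank method is unpaired, or ignores treatment order, it also gives up power that the design was chosen to provide.

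**Working it through.** **Number of completers.** SAP section 6 gives 22 required and 35% dropout: 22 / 0.65 = 33.8, rounded up to 34, which matches the stated total. The checks below use 22 completers.

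**Why participant spread is irrelevant.** Write Y = mean + participant + period + treatment + error. For one participant, the empagliflozin value minus the placebo value equals the treatment effect, plus or minus the period effect, plus the difference of two errors. The participant term is gone.

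**Scale of the assumptions.** SD 250 is from SAP section 6, which does not say what kind of SD it is. It is taken here as the SD of the paired difference, so the error SD is 250 / √2 = 176.8. The mean is not given. With two-sided alpha 0.05 and 90% power, the means implied by a 20% effect and n = 22 are:
- paired: (1.960 + 1.282) × 250 / √22 = 172.8, and 172.8 / 0.20 = 864;
- two independent groups: (1.960 + 1.282) × 250 × √(2/22) = 244.3, and 244.3 / 0.20 = 1222.

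A mean of 2500 is added as a pure assumption. The between-participant share of outcome variance then runs from 68% (CV 0.3, mean 864: SD 259.2, 259.2² / (259.2² + 176.8²)) to 98% (CV 0.5, mean 2500: SD 1250).

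**How often valid data fail the check.** Lognormal participants, exactly normal error, Shapiro-Wilk at 0.05 on the pooled volumes:

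| Assumption | Raw check fails | Raw and log both fail |
|---|---|---|
| Mean 1222, CV 0.3 | 27% | 3% |
| Mean 1222, CV 0.4 | 45% | 8% |
| Mean 1222, CV 0.5 | 63% | 12% |
| Means 864 to 2500, CV 0.3 to 0.5 | about 18 to 76% | about 3 to 15% |

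The first result column is how often a transformation is triggered. The second is how often the non-parametric branch is reached. Within-participant differences from the same trials failed in 5 to 7%.

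**What it costs.** A second set of simulations (1,000 runs per scenario) used a period-adjusted within-participant analysis as reference, with the treatment effect set for about 90% power. Participant effects were normal, skewed or two-cluster, with between/within SD ratios of 1, 2 or 4.
- Reference analysis: 89 to 92% power in every scenario. Its residuals failed the check in 4 to 6% of runs.
- Period-adjusted analysis on logs, skewed or clustered participants: 88 to 91%. Here the cost is the change of scale, not power.
- Paired signed-rank test: 86 to 90%. Paired, period-adjusted rank test: 87 to 89%. Each loses about 1 to 3 points.
- Unpaired rank-sum test, skewed or clustered participants: 5 to 77%.
- Period effect as large as the treatment effect: signed-rank without period adjustment 72%, reference 89%.
- No treatment effect: paired tests reject in about 4 to 6%, unpaired rank-sum in under 1%.

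**The case against.** The SAP names no test, threshold or pooling, so a statistician looking at plots with judgement would be within its wording. The percentages above then describe one reading of the rule. That is fair, but the object of the check is stated, and it is the outcome.

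A reader might infer that valid data would usually end in a non-parametric test. The documents do not support that. Section 9 tries a transformation first, and with lognormal participants the last branch is reached in about 3 to 15% of trials. Much higher rates appear under more skewed or two-cluster shapes (12 to 22% at an SD ratio of 1, up to 99.8% at a ratio of 4), but nothing in the documents supports those shapes.

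A reader might also infer that a rank method cannot carry the adjustment. It can: a rank test stratified by sequence respects treatment order. What stands is that the SAP does not say the fallback would do so. Nor does the fallback cause a loss of baseline adjustment for 24-hour volume, because SAP Table 1 schedules those collections at visits 3, 5, 7 and 9 and none at visits 2 or 6. That is a separate matter.

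Finally, a ratio is not foreign to the design. The planned effect is a percentage, and SD 250 belongs to the response to furosemide, not to the 24-hour volume that SAP section 5.4 analyses. If error grows with volume, logs may suit the data better. This stands as a reason to report a log-scale analysis alongside. It does not justify letting a check on the wrong quantity choose the scale.

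**Conclusion.** The point holds as a misdirected rule. Section 9 tests a quantity dominated by between-participant spread and lets it pick the scale and method for the primary endpoint. Under the lognormal assumptions above, a needless transformation is triggered in roughly 18 to 76% of trials and the non-parametric branch is reached in about 3 to 15%, against about 5% when within-participant differences are checked.

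The certain cost is that the primary effect may be reported as a ratio or in ranks, when section 9.1 promises a treatment difference in change of urine volume. Loss of power is conditional: small with a paired, period-adjusted rank test, large only if the fallback is unpaired or ignores a sizeable period effect. A reader might suspect inflated false positives, but the simulations show none. The stated sample size is unaffected. The percentages rest on assumed distributions, means, error structure and test, and exactly normal additive error is the case most favourable to the point.

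**What to change.** In SAP section 9, replace the check on outcome data with a check of residuals from the fitted crossover model with participant, period and treatment. With two periods, a participant's two residuals are equal and opposite, so inspect one value per participant.

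Pre-specify the mL scale for the primary urine volume analysis, and the log scale for the protein/creatinine and albumin/creatinine ratios. Report a log-scale analysis and a paired, sequence-stratified rank test of urine volume as sensitivity analyses only.

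The cost is SAP wording and no new data. The downside is that the mL analysis is somewhat less efficient if residual spread grows with volume, which the log-scale sensitivity analysis would show.
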